Primary carer for how many children	N/A	Number of children in household	We will derive a new parent-level variable from child-level data, counting how many children each parent cares for as primary carer, for both FDAC and non-FDAC groups.
Primary carer – Age of youngest child cared for	N/A	Age of youngest child in household	We will derive a new parent-level variable from child-level data, selecting the age of the youngest child the parent cares for as primary carer.
Number of children in the case	N/A	Number of children in household	We will derive a new case-level variable that is a count of the number of children in the case.
Age of youngest child in the case	N/A	Age of youngest child in household	We will derive a new case-level variable, calculated from the age variable in the child-level data.
Substance misuse type	Severity of parental alcohol misuse: High, Medium, Low, None, Unknown*	Substance misuse type: Drugs, Alcohol, Drugs and Alcohol, None, Unknown	FDAC data will be recoded to match non-FDAC data as follows: 1) If misusing at time of referral = No, we will code the substance misuse type as None; 2) If misusing at time of referral = Yes, we will check parental alcohol misuse and drug misuse and categorise their substance misuse type as Drugs, Alcohol, Drugs and Alcohol, or Unknown; 3) If misusing at time of referral = Unknown, we will recode the substance misuse type as Unknown
	Severity of parental drug misuse: High, Medium, Low, None, Unknown*		

*This is based on clinical judgements on substance misuse severity where guidance for the FDAC data collection tool is provided in Appendix D.

Minimum detectable effect size calculations

Power calculations were conducted in Stata 17.1 based on the anticipated matched sample size, using formulae from Dong and Maynard (2013). These formulae are presented in Appendix F. The results are presented in Table 5. The total number of non-FDAC cases will exceed the numbers prior to matching. Cases are then weighted so that there are equivalent FDAC and non-FDAC cases, so we assume equal sample sizes at analysis. Our assumptions are:

- Clustering of children within parents, with an ICC of 0.70
- No clustering of children within Local Authorities
- Variance explained by the uncoarsened covariates used in a regression model after matching, with an R-squared of 0.20 at level one and 0.10 at level two. We estimate this to provide a correlation of 0.45 and 0.32 respectively⁷

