- That 25% of children in control are reunified with their parents by the end of care-proceedings (informed by Harwin et al., 2018)
- A type one error rate of 0.05
- Power of 0.80 (a type two error rate of 0.20)
- Two tailed significance testing

There is some uncertainty on the expected sample size. Based on Harwin et al. (2018) we anticipate that each FDAC case will have a mean of 1.4 children. Our assumptions use this figure and build on estimates of expected caseloads for the implementation period (January 2021 – June 2022) collected by FDAC sites by CJI in Summer 2020. Based on updated figures concerning expected caseloads, we anticipate a sample of 300 intervention children from 215 cases.

Based on these assumptions, we expect the evaluation will be powered to detect a relative risk ratio of 1.36 (or equivalent to a 9.1 percentage point difference). No power calculations are conducted for secondary analyses, but these will have lower power as the units of analyses are at the parent and case-levels. However, as the intracluster correlation coefficient is relatively large for child-level analyses, the reduction in power will be relatively small.

Table 5 Minimum detectable effect size calculation		
Relative Risk Ratio		1.36
Baseline/Endline correlations	Child	0.45
	Parent	0.32
Intracluster correlations (ICCs)	Parent	0.70
		0.00

⁷ Our sample size calculations include estimates of the proportion of variance explained through the included covariates at each of these levels (R^2). We have converted these into pre- post-test correlations by taking the square root of the R^2 value.

Social Worker Team		0.00
Alpha		0.05
Power		0.80
One-sided or two-sided?		2
Level of intervention clustering		Parent
Average cluster size (parent)		1.40
Sample Size (children)*	Intervention	300
	Control	300
	Total	600
Sample Size (cases)	Intervention	215
	Control	215
	Total	430

* Of which, we assume half are intervention children and half are matched control children

Outcome measures

The primary and secondary outcomes will be sourced from the FDAC data collection tool for intervention cases and Local Authority administrative data for control cases. Local Authorities will already collect data on reunification but may not systematically capture parental alcohol or substance misuse, contested final hearing and use of expert witnesses. This will be included in the data collection template prepared by NatGen.

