Where $P(\text{Reunification}_{ipcs})$ is the probability of reunification. Children (i) are nested within primary carers (p), cases (c), and sites (s). The vector X_{ipcs} denotes the uncoarsened covariates. The random intercepts are represented as u_{pcs} , u_{cs} , u_s , respectively. Should the random intercept adjustments at primary-carer-level and case-level be significantly highly correlated (over .8) with each other, we will drop case-level random intercepts from the model.

The multilevel models described above will be estimated using the *melogit* command in Stata.

Additional Analysis

As a sensitivity analysis, we will fit a multilevel logistic regression model on the matched sample excluding the characteristics used in the matching in the regression model:

$$P(\text{Reunification}_{ipcs}) = \text{logit}^{-1}(\beta_0 + \beta_1 \text{Intervention}_{ipcs} + u_{pcs} + u_{cs} + u_s)$$

Secondly, we will also assess the impact of FDAC on the placement of the child (RQ6), using a categorical outcome variable that indicates 1) reunification with the child’s parents 2) placement with another relative, or 3) LA care. This will be assessed using a multilevel multinomial logistic regression.

$$P(\text{Placement}_{ipcs}) = \text{logit}^{-1}(\beta_0 + \beta_1 \text{Intervention}_{ipcs} + \beta_2 X_{ipcs} + u_{pcs} + u_{cs} + u_s)$$

As with the primary analysis, we include the uncoarsened covariates used in matching. We will present effect sizes as relative risk ratios, with 95% confidence intervals. The risk ratio will be estimated as described above.

Missing data analysis

⁸ Site refers to case locations, as shown in Table 1. Control cases will be coded as the FDAC site that serves their Local Authority (e.g. both Coventry and Warwickshire non-FDAC data will be allocated to Coventry site data). Manchester will be coded independently as there is no FDAC site.

If greater than five percent of cases are missing outcome data on the primary analysis, it is likely that missingness may impact the results of the evaluation and we will therefore consider conducting additional analysis for the primary outcome.

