We will calculate RRR as follows. First, we will calculate the conditional probabilities from the fitted coefficients of the multilevel logistic regression models by holding the covariates constant at their means.¹⁰ Second, we will then calculate relative risk ratios using the *nlcom* command in Stata, which returns the standard errors and confidence intervals of each ratio.

Exploratory Analysis

Additional analysis will be conducted to assess whether reunification can be sustained over time, as prior evidence (Harwin et al., 2019; Broadhurst et al., 2017) indicated that the greatest risk of returning to court for care proceedings are the first two years after reunification.

A prior cohort (2017 and 2018) of FDAC participants will be identified by FDAC sites. They will then share identifiers with Children Family Court Advisory and Support Service (Cafcass). Cafcass will then identify if children were returned to court for care proceedings in the subsequent three years. The analysis does not compare to a counterfactual as it will be drawing on historic data, and we do not expect comparable data for a control group to be available. This means a counterfactual cannot be constructed with matching. As this analysis will not use a counterfactual, it will not provide a causal claim, but we will compare to a national average.

¹⁰ Non-ordered categorical covariates will be represented as binary variables for each level.

We will also assess whether people who experience racism have different outcomes than those who do not. If the available data allows, we will also separate estimates for white FDAC participants and all other FDAC participants. We understand that different ethnicities may experience different impacts, and that white/non-white may mask underlying differences between different groups. However, we do not anticipate that the available sample sizes would support robust estimates for separate minority ethnicity groups.

Contextual Factors Analysis

This evaluation includes FDAC sites across multiple Local Authorities. Some FDAC sites will have been operating for over a decade, whilst others will only have launched in 2020. There are also differences in delivery models across sites. This will be explored as part of the Implementation and Process Evaluation (IPE).

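### The relative risk ratio intervals are built symmetrically on the ratio scale, so their roughly 5% error splits unevenly (about 1.3% above 1, 3.8–3.9% below 1) and borderline results can conflict with the model's own test

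*Supplement*

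**What the plan says.** All references are to the version 2.0 protocol in the Supplement.

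- **Primary model (Analysis plan, Primary Analysis).** Reunification is analysed with a multilevel logistic model fitted by melogit. The model's own test of the intervention coefficient is therefore on the log-odds scale.
- **Reported effect (Effect Size Estimation).** Binary outcomes are reported as an RRR, the predicted probability under FDAC divided by that under non-FDAC, with covariates at their means. The ratio is computed with nlcom, "which returns the standard errors and confidence intervals of each ratio". No logarithm or back-transformation appears anywhere.
- **RQ6 (Additional Analysis).** For placement: "We will present effect sizes as relative risk ratios, with 95% confidence intervals". The risk ratio there is to be estimated by the same route.
- **Error rate (Minimum detectable effect size calculations).** The power assumptions include "A type one error rate of 0.05" and "Two tailed significance testing". The study is said to be "powered to detect a relative risk ratio of 1.36 (or equivalent to a 9.1 percentage point difference".
- **Decision rule.** The analysis plan does not say whether significance for RQ1 is judged from the coefficient or from the RRR interval.

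**The concern.** The standard error of a ratio grows with the ratio. An interval of estimate ± 1.96 SE on the ratio scale is therefore too wide on the side facing 1 when the estimate is above 1, and too narrow on that side when it is below 1. The log-odds test in the same model does not share this asymmetry.

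The RRR and its interval are the headline result, and readers will look to see whether the interval includes 1. For reunification, benefit is an RRR above 1, which is the strict side, so power is lost. For contested hearings and expert use, benefit is an RRR below 1, which is the lenient side. The plan does not say which result governs when the interval and the coefficient test differ.

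**Working it through.** **Inputs, all from Minimum detectable effect size calculations.** "Clustering of children within parents, with an ICC of 0.70"; R-squared 0.20 at level one and 0.10 at level two; 1.4 children per case; 430 cases in two equal groups (P = 0.5); "That 25% of children in control are reunified with their parents by the end of care-proceedings"; two-sided alpha 0.05; "Power of 0.80 (a type two error rate of 0.20".

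**1. Reproduce the stated 1.36.**
- SE of the standardised effect = √{[0.70 × (1 − 0.10) + 0.30 × (1 − 0.20)/1.4] / (0.25 × 430)} = 0.0863.
- The multiplier t(0.975) + t(0.80) is 2.808, so MDES = 0.2425.
- OR = exp(0.2425 × π/√3) = 1.552.
- RRR = 1.552 / (0.75 + 0.25 × 1.552) = 1.364, or 9.1 percentage points. This matches the plan, and taking 12, 14 or 31 Local Authorities makes no difference.
- This uses the conventional placement of the two R-squared values and the exponential function. Appendix F as printed differs in both respects, which is a separate matter.

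**2. Implied precision.**
- SE(log OR) = 0.0863 × π/√3 = 0.157.
- At the null with 25% reunified, SE(log RRR) = 0.75 × 0.157 = 0.117.
- Working back from 80% power at 1.36 instead, SE(log RRR) = ln(1.36)/2.8016 = 0.110.
- So s is about 0.11 to 0.12.

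**3. Tails of the ratio-scale interval under no effect.** The interval is RRR × (1 ± 1.96s). It lies wholly above 1 when ln RRR > −ln(1 − 1.96s), and wholly below 1 when ln RRR < −ln(1 + 1.96s).

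| s | Wholly above 1 | Wholly below 1 | Total |
|---|---|---|---|
| 0.110 | 1.4% | 3.8% | 5.2% |
| 0.117 | 1.3% | 3.9% | 5.2% |

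A simulation of a two-arm logistic comparison (2,000,000 draws, SE(log OR) 0.157, 25% in both arms) gave 1.2% and 3.8% for the ratio-scale interval, 2.4% and 2.4% for the log-RRR interval, and 2.5% and 2.4% for the coefficient test.

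**4. Power at the target.** With s = 0.110 the upper threshold is −ln(1 − 1.96 × 0.110) = 0.242, and ln(1.36) = 0.307. The ratio-scale interval excludes 1 with probability Φ((0.307 − 0.242)/0.110), about 72% to 73%. The log-scale interval has 80%. In the logistic simulation at OR 1.55 the figures were 76.9% against 83.7% for the model test. Either way the gap is about 7 to 8 points.

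**5. Where the two results conflict.** Holding s at 0.1175, a log-scale interval excludes 1 once the estimate passes exp(0.230) = 1.26 or exp(−0.230) = 0.79. The ratio-scale interval needs 1/(1 − 0.230) = 1.30 above, but only 1/(1 + 0.230) = 0.81 below. Two examples at the plan's precision:

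| Reunified, control v FDAC | Coefficient test | RRR | Ratio-scale interval | Log-scale interval |
|---|---|---|---|---|
| 25% v 31.7% | z = 2.17, p = 0.030 | 1.27 | 0.996 to 1.536 | 1.02 to 1.57 |
| 25% v 20.0% | z = −1.77, p = 0.076 | 0.80 | 0.600 to 0.997 | 0.62 to 1.02 |

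Under no effect, interval and test disagreed in 2.6% of simulated trials.

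**6. Sensitivity to the baseline rate.** With the same SE(log OR), control rates from 15% to 50% gave tails from 1.1%/4.0% to 1.6%/3.3%. For a case-level outcome with 215 cases per arm and no covariates, s = √[2(1 − p)/(215p)]. The tails are about 1.0%/4.3% at an assumed 30% rate, 1.5%/3.6% at 50% and 1.8%/3.2% at 70%. The direction is the same throughout, but the size shrinks as the outcome becomes more common.

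**The case against.** **In the plan's defence.** The method is named, reproducible and valid to first order. The point estimate is unaffected and total error is about 5%. For the primary outcome the distortion is conservative: a false claim of benefit is less likely than the nominal 2.5%. All of this stands, and it makes the point a refinement of the interval rather than a failure of the analysis. It does not remove the uneven split or the possible conflict with the coefficient test.

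**Stronger readings that the documents do not support:**

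- *The interval breaches the stated two-tailed 5% test.* The documents give 5%, two-tailed, as a power assumption. They never promise 2.5% per side, and the total is preserved.
- *The plan has two competing decision rules, one resting on nlcom's default p-value, which tests a ratio of 0.* No decision rule is tied to the RRR interval, and nlcom is cited only for standard errors and intervals. The plan simply does not name its test.
- *Power falls by around 14 points.* A clustered simulation without covariates shows this (44% against 58%), but its average SE(log RRR) is about 0.15 to 0.16. That shortfall against 80% is mostly a separate question of precision.
- *An observed RRR of 1.36 would itself be reported as including 1.* That needs an SE of about 0.14, which gives 0.99 to 1.73. At 0.11 the intervals are 1.07 to 1.65 (ratio scale) and 1.10 to 1.69 (log scale), and both exclude 1.
- *Every secondary outcome is tilted towards FDAC.* No baseline rates are given for them, so the size is unknown. For RQ2 even the direction is open: Outcome measures codes 1 as still misusing, while Table 2 and model (1) are written for cessation. The count of expert types is estimated through meglm and lies outside this point.

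**Conclusion.** The concern holds in limited form. On the natural reading of Effect Size Estimation, the RRR intervals are symmetric on the ratio scale. At the plan's own precision they divide an error of about 5% into roughly 1.3% above 1 and 3.8% to 3.9% below 1. At the target effect the reported interval excludes 1 about 7 to 8 points less often than the log-scale interval or the model test. Conflicts with the coefficient test are confined to borderline estimates. For contested hearings, expert use, and misuse if coded as in Outcome measures, the lenient side favours FDAC by an amount that cannot be fixed from the documents.

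This rests on three assumptions: nlcom is given the untransformed ratio; the SE is the one implied by the detectable-effect inputs, since none is stated; and the calculations simplify the weighted multilevel model with covariates. A larger SE than planned would widen the asymmetry.

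**What to change.** In Effect Size Estimation, apply nlcom to ln(P(FDAC)/P(non-FDAC)) and exponentiate the estimate and both limits. Do this for every RRR obtained by this route, including RQ6. Add a sentence stating that the two-sided 5% test for RQ1 is the test of the intervention coefficient in the melogit model.

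The cost is one line of Stata code and two sentences of text, with no new data and no change to the point estimates. On the log scale the two tails are close to equal (2.4% each in the simulation), so the direction in which an outcome is coded no longer decides which side is lenient.

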In addition, COVID-19 has had a significant impact on social care, both within FDAC sites and in Local Authorities more generally. The impact of COVID-19 varies across some sites. Existing sites have not been able to take on new cases or have had staff diverted to other social care work. New sites have had difficulties with recruitment and have had to delay their launch dates. At this stage, the full impacts of COVID-19 on FDAC sites are not known, but further contextual information will be provided in the evaluation report.

This evaluation will not be powered sufficiently to estimate variation in the effect across sites, but variation in implementation will be explored across sites as part of the IPE.

Implementation and process evaluation

The IPE will use a qualitative methodology; interviews in sampled case study areas, to understand the advantages and disadvantages of particular FDAC iterations and variations and gather information on barriers and facilitators to successful implementation and delivery. It will also explore how perceived impacts from the FDAC courts compare with non-FDAC care proceedings as usual. Drawing on the work undertaken for the feasibility study to refine the programme theory for the FDAC model, the IPE will also explore (see Appendix E):

- Views and experiences of implementing FDAC;
- Awareness, understanding and commitment to the FDAC approach;
- Parental engagement, views and experiences of court proceedings;
- Staff and practitioner views and experiences of delivering the model, working across multidisciplinary teams and engaging families; and
- Views on the perceived impact of FDAC on families, the courts, practitioners and wider CJS.

With stakeholders and staff, data collection will focus on commitment, buy-in and understanding of FDAC, views on whether the necessary procedures, processes and resources are in place, the skills and competencies of professionals to effectively deliver FDAC (including for example, selection to receive FDAC), the effectiveness of judicial oversight and partnership working and views on parental engagement, experiences and skills development.

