Interviews will last up to 60 minutes and will be carried out via phone, web or face-to-face, depending on participant preference and social distancing requirements at the time of data collection. Interviews will be audio-recorded and transcribed verbatim to facilitate robust analysis.

All recordings will be managed using NatCen's Framework approach. This will involve managing interview data and conducting case- and theme-based analysis. Key topics emerging from the transcripts will first be identified. A thematic framework will then be developed and used to organise the data from each participant. Then the coded data will be reviewed in detail, drawing out the range of experiences or views, identifying similarities and differences, developing and testing hypotheses, and interrogating data to seek to explain patterns and findings.

Based on the systematic analysis of the IPE data, a short report will be drafted and submitted to the WWCS and CJI in the Autumn of 2021. The report will highlight key findings thematically, examining similarities and differences between case study areas and participant groups. A summary of IPE findings will also be included in the final report, due to be submitted in September 2022.

Cost evaluation

Costs will be estimated based on the delivery costs of the intervention. Each FDAC site manager will be provided with pro-forma to complete in Summer 2022 covering costs incurred in the financial year 2020/2021. This will assign costs to different categories, such

as setup costs (e.g. preparation costs, facilities, overheads) and delivery costs (e.g. salary costs, training and support costs, assessment and legal fees).

Sites will be asked to provide this data for a one financial year. The set-up costs will be estimated only for sites that have launched in March 2020 or after. Costs will be estimated from the perspective of the LA on a per-child basis by dividing the total annual cost (i.e. setup and delivery costs) by the number of children who go through FDAC care proceedings.

Ethics & Participation

Ethical clearance was sought from NatCen's ethics committee in June 2020. Ethical approval was granted on 25th June 2020 subject to the condition of agreeing safeguarding procedures with Local Authorities and providing support for NatCen staff working on the evaluation.

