Interviews will last up to 60 minutes and will be carried out via phone, web or face-to-face, depending on participant preference and social distancing requirements at the time of data collection. Interviews will be audio-recorded and transcribed verbatim to facilitate robust analysis.

All recordings will be managed using NatCen's Framework approach. This will involve managing interview data and conducting case- and theme-based analysis. Key topics emerging from the transcripts will first be identified. A thematic framework will then be developed and used to organise the data from each participant. Then the coded data will be reviewed in detail, drawing out the range of experiences or views, identifying similarities and differences, developing and testing hypotheses, and interrogating data to seek to explain patterns and findings.

Based on the systematic analysis of the IPE data, a short report will be drafted and submitted to the WWCS and CJI in the Autumn of 2021. The report will highlight key findings thematically, examining similarities and differences between case study areas and participant groups. A summary of IPE findings will also be included in the final report, due to be submitted in September 2022.

Cost evaluation

Costs will be estimated based on the delivery costs of the intervention. Each FDAC site manager will be provided with pro-forma to complete in Autumn 2021 covering costs incurred in the last twelve months. This will assign costs to different categories, such as staff costs, fixed costs (e.g. purchase of equipment), marginal costs (such as rent) and set-up

costs (where appropriate for newer sites, which may include staff recruitment and training costs).

Sites will be asked to provide this data for a one-year period. The set-up costs will be estimated only for sites that have launched since March 2020. Set-up costs will be averaged over three years to provide a more realistic estimate of the annual running costs of FDAC. This is because interventions tend to have higher costs in the first year of delivery that would otherwise provide an unrealistic estimate of what the ongoing costs for the intervention would be. Costs will be estimated from the perspective of the LA on a per-child basis by dividing the total annual cost by the number of children who go through FDAC care proceedings.

Ethics & Participation

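### The cost-per-child rule charges newer sites' 2020/21 set-up spending in full to one atypical year and leaves the denominator's period undefined; with same-year children as denominator it overstates ongoing cost

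*Supplement*

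**What the plan says.** In protocol version 2.0, Cost evaluation, each FDAC site manager receives a "pro-forma to complete in Summer 2022 covering costs incurred in the financial year 2020/2021". The section then limits the data to that period: "Sites will be asked to provide this data for a one financial year". The pro-forma sorts spending into categories. Set-up is exemplified by preparation, facilities and overheads; delivery by salaries, training and support, and assessment and legal fees.

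On which sites contribute set-up: "The set-up costs will be estimated only for sites that have launched in March 2020 or after". The unit cost is then obtained "by dividing the total annual cost (i.e. setup and delivery costs) by the number of children who go through FDAC care proceedings". The section describes no spreading of set-up over time, no figure without set-up, no site-specific figure and no sensitivity analysis. It does not say over what period the children are counted.

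The Contextual Factors Analysis section describes the sites: "Some FDAC sites will have been operating for over a decade, whilst others will only have launched in 2020". On the pandemic it says: "Existing sites have not been able to take on new cases or have had staff diverted to other social care work". It adds: "New sites have had difficulties with recruitment and have had to delay their launch dates".

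**The concern.** The one-off part of set-up spending serves families over several years. Charging all of it to the first year's children gives the cost of launching a site, not of running one. Because set-up counts only at newer sites, the result is also a blend of two kinds of site whose proportions depend on how many happened to launch in time.

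The chosen year makes this worse. The sentences on restricted intake and delayed launches also stand in version 1.0, dated 17 December 2020, so they describe conditions within financial year 2020/21 (taking that as April to March). Fewer children over staffing that does not fall in proportion raises the unit cost.

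Cost per child is the only output of the cost evaluation. No cost-effectiveness ratio is planned and no impact estimate is affected, but a commissioner has no other cost figure to use.

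**Working it through.** The plan gives no cost figure to reproduce, and no set-up amount or annual number of children. Only ratios can be worked out, with the inputs below assumed.

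**1. Set-up at one new site, same-year denominator.** Let S be set-up cost, D delivery cost and n the year's children.

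- Rule as written: (S + D)/n
- Set-up spread over three years: (S/3 + D)/n
- Ratio, with q = S/(S + D): 1/(1 − 2q/3)

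The three-year period is the one used in version 1.0 (Cost evaluation): "Set-up costs will be averaged over three years to provide a more realistic estimate of the annual running costs of FDAC". It serves here only as a benchmark.

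**2. New and older sites together.** Let w be the new sites' share of all delivery cost and s = q/(1 − q). The ratio becomes (1 + ws)/(1 + ws/3).

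| Set-up share q (assumed) | s | New site alone | All sites, w = 0.25 (assumed) |
|---|---|---|---|
| 10% | 0.111 | 1/0.933 = 1.07 | 1.028/1.009 = 1.02 |
| 25% | 0.333 | 1/0.833 = 1.20 | 1.083/1.028 = 1.05 |
| 40% | 0.667 | 1/0.733 = 1.36 | 1.167/1.056 = 1.11 |

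**3. Period of the denominator.** The study window in the Participants section, October 2019 to June 2022, is 33 months. A one-year numerator over 33 months of children, at even throughput, divides each ratio by 33/12 = 2.75. The three all-site values become about 0.37, 0.38 and 0.40. Even the largest single-site value gives 1.36/2.75 = 0.50. On that reading the figure is far too low.

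**4. Throughput.** If intake is a fraction f of normal and delivery spending a fraction g, delivery cost per child changes by g/f. With f = 0.8 (assumed):

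- g = 1.0 gives 1.25
- g = 0.9 gives 1.13
- g = 0.8 gives 1.00

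The effect depends on how far spending fell with intake, and the documents give neither f nor g.

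**5. What set-up contains.** The plan places facilities and overheads under set-up, and these can recur every year. Suppose q = 25% and half of that recurs (assumed). The appropriate annual cost, as a fraction of the first-year total, is 0.75 + 0.125 + 0.125/3 = 0.917.

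- Rule as written: 1/0.917 = 1.09
- Whole category spread over three years: (0.75 + 0.25/3)/0.917 = 0.833/0.917 = 0.91

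Spreading everything labelled set-up would replace an overstatement with an understatement of similar size.

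**The case against.** A reader might infer that the figure is bound to overstate what FDAC costs. The documents do not go that far. The denominator has no stated period, and a study-window count would reverse the sign. Same-year children is the natural partner of an annual cost, but it is not written down.

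A reader might also take all set-up spending to be charged. Only what was incurred in 2020/21 at sites launched in March 2020 or after enters; preparation before that year falls outside the return, and older sites dilute the total.

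A third tempting reading is that halved or reduced intake inflated unit cost by a third or more. That needs unchanged salaries. The sentences that report restricted intake also report diverted staff and recruitment difficulties, either of which could have lowered FDAC delivery cost. The section adds that effects varied by site and were not fully known.

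The set-up category also cuts the other way. If older sites' facilities and overheads are excluded because they are labelled set-up, those sites' costs are understated.

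Finally, the pro-forma already separates the two categories, and the plan promises further COVID context in the report. Separate reporting is therefore possible, but the plan does not commit to it. These points limit size and certainty. They do not supply the missing denominator or justify charging a one-off outlay to one year.

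**Conclusion.** The point holds, conditionally. With same-year children as denominator, any positive one-off set-up cost makes the rule exceed the ongoing cost per child. The illustrative excess is 1.07 to 1.36 times at a new site, and about 1.02 to 1.11 times across sites if new sites carry a quarter of delivery cost. Both ranges rest on assumed set-up shares of 10% to 40%, all of it one-off, against a three-year benchmark. The actual size cannot be had from the documents.

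The choice of 2020/21 probably adds to this, but the net effect of lower intake and possibly lower staffing cost is unknown. If children were counted over the whole study window, the direction would reverse, so the undefined period is itself a defect. The matter is confined to the cost evaluation.

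**What to change.** - Split the set-up category into one-off items and recurring facilities and overheads, and count the recurring items as running costs at all sites.
- Annualise only the one-off part, over a stated period such as three years.
- Report cost per child with and without annualised set-up.
- Define the denominator as children in FDAC proceedings at that site in the same financial year as the costs.
- State 2020/21 as a limitation. Optionally add a sensitivity figure using average annual throughput over the study window. It would not represent normal throughput: 28 of the 33 months fall in or after March 2020, when the plan dates the start of disruption, and the impact data hold only cases with a final hearing by October 2022.

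The cost is mainly wording and recalculation. Sites may need to clarify which overheads recur; as the pro-forma was due in Summer 2022 and version 2.0 is dated 1 November 2022, that would probably be a follow-up query. Removing months before launch would need dated costs, which a single annual return may not give, so it is not required here. The report would carry two or three unit costs.
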